5.4 Selection of Subjects

Selection of Subjects: Patients with a malignant glioma who plan to undergo standard RT with concomitant daily temozolomide (TMZ) therapy

Inclusion Criteria:

- Patients must have histologically-confirmed, newly-diagnosed malignant glioma (glioblastoma, gliosarcoma, anaplastic astrocytoma, anaplastic oligoastrocytoma, anaplastic pleomorphic xanthoastrocytoma, or anaplastic oligodendroglioma) and are scheduled to receive radiotherapy (for a total of 54-60 Gy) and concomitant daily temozolomide therapy (at a dose of 75 mg/m² for one complete 6-week cycle).
- 2. Age ≥ 18 years
- 3. Karnofsky ≥ 60% or ECOG 0-2
- 4. For patients on higher than physiological level of corticosteroids, they must have been on a stable dose for 1 week prior to initiating study drug, and the dose should not be escalated over entry dose level, if clinically possible
- 5. Ability and willingness to give informed consent
- 6. Female patients of childbearing potential must have a negative pregnancy test at Screening
- 7. Female patients of childbearing potential must agree to use an acceptable method of birth control (please refer to the attached document, Birth Control Recommendations (Appendix 18.5)) from the signing of

- informed consent form and to continue its use during the study and for at least 90 days after the final dose
- Male patients must agree to use an acceptable form of birth control (please refer to the attached document, Birth Control Recommendations (Appendix 18.5) from study Day 1 through at least 90 days after the final dose
- 9. Hematocrit >29%, ANC >1,000 cells/mm³, platelets >100,000 cells/ mm³
- 10. Serum creatinine <1.4 mg/dl, bilirubin <1.5 times upper limit of normal
- 11. Aspartate aminotransferase (AST) \leq 2.5 x upper limit of normal range (ULN). For subjects with known liver metastases \leq 5 x ULN, and alanine aminotransferase (ALT) \leq 2.5 x ULN. For subjects with known liver metastases \leq 5 x ULN

Exclusion Criteria:

- Co-medications that may interact with rolapitant as reviewed by Duke Preston Robert Tisch Brain Tumor investigator pharmacist
- Co-medications that are contraindicated in patients on rolapitant including pimozide, thioridazine, carbamazepine, colchicine, dabigatran (Pradaxa), edoxaban (Savaysa), fosphenytoin, metoprolol, phenobarbital, phenytoin, primidone, and warfarin
- 3. Inability or unwillingness to cooperate with the study procedures

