9.6 Randomization

A permuted block randomization will be used to assign patients, in an unblinded fashion, to one of two treatment sequences as described in Section 9.1. A 1:1 allocation ratio will be used.

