15.4.1 Variable

Complete response (CR) rate associated with rolapitant plus ondansetron and that associated with ondansetron during the first two weeks of RT and concomitant TMZ is defined as the proportion of patients with no emetic episode or use of rescue medication while receiving radiation and concomitant TMZ. The CR rate will be assessed via the modified MASCC Antiemesis Tool (MAT).¹⁷

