15.4.2 Statistical Hypothesis, Model, and Method of Analysis

As the primary analysis, a chi-square test will compare treatment regimens (ondansetron alone vs rolapitant + ondansetron) with respect to the proportion of patients who experience a CR during the first 2 weeks of RT and TMZ treatment. As an additional analysis, logistic regression will assess the effect of potential confounders on this relationship. Among the covariates that will be considered is the dose of decadron administered during the 2 weeks of RT and TMZ treatment.

As an exploratory analysis, a generalized linear model with a logit link that accounts for correlation between the CR status observed during the first and second treatment period within the same patient will be used to assess the impact of period, treatment, and their interaction. The purpose of this latter analysis is to assess whether the incremental effect of combination treatment relative to ondansetron alone is the same whether rolapitant is administered during the first period (i.e. first 3 weeks) or the second period (i.e. the second 3-week treatment regimen). It should be noted that this test will have low power to detect a clinically meaningful interaction effect. Within the context of the generalized linear model described above, the impact of covariates on CR rate will be explored. Included among these covariates will be the dose of decadron administer during that segment of the treatment regimen.

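### Section 15.4.2 treats decadron dose given after randomisation as a potential confounder of the CR comparison. Adjust for entry dose instead, and report on-treatment dose as a labelled, non-causal sensitivity check (minor; supportive and exploratory models only).

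*Combined protocol and SAP*

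**What the plan says.** The primary analysis in Section 15.4.2 is an unadjusted chi-square test of CR over the first two weeks of radiation and temozolomide. Section 15.4.1 defines the CR rate as "the proportion of patients with no emetic episode or use of rescue medication while receiving radiation and concomitant TMZ".

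Two further models follow in Section 15.4.2:

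- **Additional logistic regression.** "As an additional analysis, logistic regression will assess the effect of potential confounders on this relationship". The only covariate named is decadron dose over the same two weeks: "Among the covariates that will be considered is the dose of decadron administered during the 2 weeks of RT and TMZ treatment".
- **Exploratory two-period logit model.** It allows for within-patient correlation and examines period, treatment and their interaction. Within it, "the impact of covariates on CR rate will be explored", and "Included among these covariates will be the dose of decadron administer during that segment of the treatment regimen".

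Assignment is open label (Section 9.6): "A permuted block randomization will be used to assign patients, in an unblinded fashion". Inclusion 4 in Section 5.4 says of patients on more than a physiological corticosteroid level that "they must have been on a stable dose for 1 week prior to initiating study drug", and that "the dose should not be escalated over entry dose level, if clinically possible". Section 9.4.3 allows corticosteroids for cerebral swelling. Section 9.4.1 leaves the type of rescue antiemetic to the investigator. Section 12 has steroids recorded at screening.

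The plan does not say what the adjusted treatment effect is meant to estimate, and does not restrict on-treatment dose to a descriptive role.

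**The concern.** A confounder must precede, or at least not result from, the exposure. Here the exposure is a randomised assignment and the dose is accumulated after it. Any difference between arms in that dose beyond chance is a consequence of assignment or of what followed, not a pre-existing imbalance.

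Two results could be misread:

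1. **The adjusted treatment OR.** It could be presented as corrected for confounding when it conditions on a post-randomisation variable. It can shift if dose responds to symptoms differently by arm, or if dose responds to assignment and is also linked to CR.
2. **The decadron OR.** If dose is raised because a patient is unwell, the coefficient shows that failures received more steroid, not that steroid changed CR.

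The protocol limits dose changes but does not exclude them, since escalation is discouraged only where clinically possible. Section 15.4 concedes that 57 patients may no longer give adequate power, so readers may look harder at the supportive models.

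**Working it through.** **Step 1. The plan's own figures.** For n per arm and one-sided α = 0.05:

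power = Φ[(p1 − p0 − 1.645·s0)/s1], with s0 = √[2p̄(1−p̄)/n] and s1 = √{[p0(1−p0) + p1(1−p1)]/n}.

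- Original design (Section 15.7.1: 152 patients, n = 76, 75% vs 90%): s0 = 0.0616, s1 = 0.0604, power = 78.9%.
- Modified design (Section 15.7.2: 57 patients, n = 28.5, 75% vs 97%): s0 = 0.0919, s1 = 0.0872, power = 78.5%. For 63% vs 90% it is 78.8%.

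The stated 80% is reproduced within 2 points. It belongs to the unadjusted test, so the covariate choice does not touch it.

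**Step 2. Treatment OR, binary dose change.** Take CR 75% vs 90% from Section 15.7.1. The true OR is (0.90/0.10)/(0.75/0.25) = 3.0. Let D be any decadron increase in the window. All behaviour of D is assumed, with P(D | CR) = 0.10 in both arms and no steroid effect. Large-sample logistic fits of CR on treatment and D give:

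| P(D given failure), combination / ondansetron | Adjusted treatment OR |
|---|---|
| 0.40 / 0.40 | 3.00 |
| 0.20 / 0.20 | 3.00 |
| 0.20 / 0.60 | 2.49 |
| 0.20 / 0.40 | 2.82 |
| 0.40 / 0.20 | 3.15 |
| 0.60 / 0.20 | 3.43 |

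An equal response in both arms causes no shift. An unequal response moves the OR by −17% (2.49/3.0) to +14% (3.43/3.0).

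**Step 3. Treatment OR, continuous dose.** In a second assumed model, dose rises by d SD of entry dose after a failure and shifts by a SD according to assignment. Simulation of 400,000 patients per scenario gives these ORs adjusted for on-treatment dose:

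| d, a | True OR 3.0 | True OR 1.0 |
|---|---|---|
| 0.5, −0.3 | 2.7 | 0.89 |
| 0.5, −0.6 | 2.3 | 0.79 |
| 1.0, −0.3 | 2.3 | 0.78 |
| 1.0, −0.6 | 1.9 | 0.62 |

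With a = 0 or d = 0 there is no shift. Adjusting for entry dose gives about 3.0 and 1.0 throughout; in this model entry dose has no relation to CR.

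**Step 4. Sampling error at N = 57.** With 28 on ondansetron (21 CR, 7 failures) and 29 on the combination (26.1 CR, 2.9 failures):

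SE(log OR) = √(1/21 + 1/7 + 1/26.1 + 1/2.9) = 0.757, so the 95% CI around 3.0 is 0.68 to 13.2. The shifts in Steps 2 and 3 are small beside this.

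**Step 5. The decadron OR.** Assume no steroid effect, with increases in 40% of failures and 10% of responders:

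OR for CR = (0.10/0.90)/(0.40/0.60) = 0.167.

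At N = 57 there are 9.9 failures (3.96 with D) and 47.1 responders (4.71 with D). SE = √(1/3.96 + 1/5.94 + 1/4.71 + 1/42.39) = 0.810, z = ln(0.167)/0.810 = −2.21, approximate 95% CI 0.03 to 0.82. If only 20% of failures have an increase, the OR is 0.44 with 95% CI 0.07 to 2.8.

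**The case against.** **Rank of the models.** One model is additional and the other exploratory, and decadron is only to be considered. No decision or alpha rests on either. This stands, and it is why the point is minor.

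**Departure from 3.0 is not a clean measure of bias.** The OR is non-collapsible. If entry dose (standardised, normal) had an assumed OR for CR of 2 or 3 per SD, adjusting for it would itself move 3.0 to 3.23 or 3.59 (+8% or +20%). This stands: the ranges in Steps 2 and 3 show that a shift is possible and do not predict its size.

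**On-treatment dose has a legitimate use.** Dexamethasone (decadron) was part of the antiemetic regimen in the phase 3 rolapitant trials described in Section 7.2.2. In an open-label trial, unequal steroid use is a credible co-intervention, and these models are the plan's only modelled check on it. Entry dose cannot detect it. This stands, and the fix keeps the check.

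**Stronger readings that the documents do not support:**

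- A reader might infer that the primary result is biased. It is not, because the chi-square test uses no covariate.
- A reader might infer that steroids will serve as rescue. Section 9.4.1 does not exclude this, but no section names a corticosteroid as rescue, and the example in Section 9.4.2 is ondansetron. Section 7.2 gives no pharmacokinetic reason to change dexamethasone dose with rolapitant.
- A reader might infer a path through nausea, since nausea alone is not a CR failure. But decadron given to treat nausea would be rescue use, which Section 15.4.1 counts as failure. That path needs an increase prompted by nausea yet attributed to something else, so no figure is put on it here.

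**Conclusion.** The point holds as a minor correction to the supportive and exploratory analyses. A dose given after open-label randomisation, in the outcome window, is not a confounder of the randomised first-period comparison. Conditioning on it can shift the treatment OR under some dose behaviours and not under others. The illustrated ranges around a true OR of 3.0 (2.5 to 3.4, and 1.9 to 2.7) come from different assumptions. The documents give no data on how dose responds to assignment or symptoms, so actual bias is unknown in size and direction and may be zero.

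Interpretation of the decadron coefficient is the clearer weakness. Under one assumed pattern of symptom response it would be nominally significant at 57 patients with no steroid effect at all; under a milder pattern it would not.

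**What to change.** In Section 15.4.2:

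1. Name entry decadron dose, defined as the last dose recorded before randomisation, as the steroid covariate for the adjusted treatment effect in both models. State that in the two-period model it is constant within a patient and so adjusts only between patients.
2. Summarise on-treatment decadron dose by arm and period, where recorded.
3. If a model with on-treatment dose is fitted, report it beside the entry-dose model as a sensitivity check on steroid co-intervention. Label it post-randomisation and non-causal, and do not describe the dose as a confounder or its coefficient as an effect on CR.

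**Cost.** The text change is small, but data availability must be checked. Section 12 has steroids recorded at screening and concomitant medications confirmed within two weeks of starting radiation, and Inclusion 4 requires knowledge of the entry dose for patients above physiological level. None of this shows that a numeric dose was entered for every patient. Nor do the documents place randomisation relative to that confirmation. Table 7, as it reads in the available text, marks concomitant medications at screening and week 1 only, so capture of on-treatment dose needs the same check.

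**Downside.** Entry dose cannot reflect changes during treatment or differences between periods. The summary and the labelled sensitivity model cover these only descriptively.

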17. Patient must not have been dosed with test drug or blinded study drug in another investigational study within 30 days or 5 half-lives of the biologic activity of the test drug, whichever is longer, before the time of first study dose

18. Patient who is receiving investigational agent(s) as part of another clinical study at the time of screening or who anticipates receiving investigational agent(s) during their scheduled radiotherapy and concomitant daily temozolomide therapy. (Please refer to study Memo to File regarding exceptions to this exclusion criteria)

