Metabolism - Rolapitant is metabolized primarily by CYP3A4 to form a major active metabolite, M19 (C4-pyrrolidine-hydroxylated rolapitant). In a mass balance study, the metabolite M19 was the major circulating metabolite. The formation of M19 was significantly delayed with the median T_{max} of 120 hrs. (range: 24-168 hours) and the mean half-life of M19 was 158 hours. The exposure ratio of M19 to rolapitant was approximately 50% in plasma.

Excretion - Rolapitant is eliminated primarily through the hepatic/biliary route. Following administration of a single oral 180 mg dose of $[^{14}C]$ -rolapitant, on average 14.2% (range 9% to 20%) and 73% (range 52% to 89%)

of the dose was recovered in the urine and feces, respectively over ~ 6 weeks. In pooled samples collected over 2 weeks, 8.3% of the dose was recovered in the urine primarily as metabolites and 37.8% of the dose was recovered in the feces primarily as unchanged rolapitant. Unchanged rolapitant or M19 were not found in pooled urine sample.

Specific Populations - Age, Sex and Race/Ethnicity - Population pharmacokinetic analyses indicated that age, sex and race had no significant impact on the pharmacokinetics of rolapitant.

Pregnancy: There are no available data on rolapitant use in pregnant women to inform any drug-associated risks. In animal reproduction studies, there were no teratogenic or embryo-fetal effects observed with oral administration of rolapitant hydrochloride in rats and rabbits during the period of organogenesis at doses up to 1.2 times and 2.9 times, respectively, the maximum recommended human dose (MRHD). In the U.S. general population, the estimated background risk of major birth defects and miscarriage in clinically recognized pregnancies is 2% to 4% and 15% to 20%, respectively.

Hepatic Impairment- Following administrations of a single dose of 180 mg rolapitant to patients with mild hepatic impairment (Child-Pugh Class A), the pharmacokinetics of rolapitant were comparable with those of healthy subjects. In patients with moderate hepatic impairment (Child-Pugh Class B), the mean C_{max} was 25% lower while mean AUC of rolapitant was similar compared to those of healthy subjects. The median T_{max} for M19 was delayed to 204 hours in patients with mild or moderate hepatic impairment compared to 168 hours in healthy subjects. The pharmacokinetics of rolapitant was not studied in patients with severe hepatic impairment (Child-Pugh Class C).

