9.7 Rationale for Selection of Dose, Regimen, and Treatment Duration

Rolapitant is an FDA-approved, novel long-acting new highly selective NK_1 receptor antagonist (RA) that is designed to be given in combination with a $5HT_3$ -RA (i.e. ondansetron) to prevent CINV. Based on preclinical data and the half- life (170 hrs.) described previously and below, **one oral** rolapitant dose of 180 mg will be administered in combination with oral daily ondansetron at 8 mg/day to provided antiemetic coverage for 3 weeks of radiation (3-half-lives for rolapitant). Sequence A involves administration of ondansetron alone for 3 weeks followed by the use of rolapitant X 1 dose plus ondansetron for 3 weeks; whereas sequence B involves the use of rolapitant X 1 dose plus ondansetron for 3 weeks followed by 3 weeks of ondansetron alone. For the rolapitant plus ondansetron weeks (1 or 4), patients will self-administer the oral rolapitant pill 1-2 hours before the first fraction of radiation on the planned week (see schema). The rolapitant doses will be supplied by TerSera.

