15.7 Sample Size Calculation

15.7.1 Original Study Design

One hundred seventy (170) glioma patients will be enrolled with the expectation that 160 patients will be randomized to receive one of two treatment sequences of anti-emetic therapy for the prevention of nausea and vomiting associated with RT and concomitant TMZ. A permutated block randomization with an allocation ratio of 1:1 will be used to assign patients to sequence A or B. Sequence A involves a 3-week regimen of daily ondansetron followed by a 3-week regimen consisting of rolapitant (day 22 only) and daily ondansetron; whereas Sequence B involves a 3-week regimen of rolapitant (day 1 only) and daily ondansetron followed by a 3-week regimen of daily ondansetron. The study has one primary and one KEY secondary endpoint: CR rate and patient overall preference for ondansetron treatment with or without rolapitant. Though the primary CR rate endpoint will focus on treatment during the first 2 weeks of RT and TMZ, a crossover design is proposed so that a patient will experience both modes of treatment, and be equipped to make a comparative assessment of preference.

Power Calculations for Complete Response, Primary Endpoint: The power of the comparison of ondansetron and the combination of ondansetron and rolapitant relative to the CR rate during the initial 2 weeks of treatment with RT and TMZ will be considered here. This comparison will focus on the anti-emetic experience during the first regimen of the two treatment regimens that the patient will receive. Let

p₁ = overall complete response rate for the first 2 weeks of treatment with the combination antiemetic regimen, and

 p_0 = overall complete response rate during the first 2 weeks of treatment with ondansetron alone.

The hypothesis that will be assessed is whether the CR rate with combination treatment is greater than that with ondansetron alone. Specifically, the hypothesis that will be tested is as follows:

 H_0 : $p_1 \le p_0$ versus H1: $p_1 > p_0$

Temozolomide prescribing information reports a vomiting rate of 20% with concomitant RT + TMZ. Anti-emetic treatment failure includes the occurrence of vomiting or the use of an anti-emetic for nausea and/or vomiting. Therefore, we anticipate that approximately 25% of patients receiving ondansetron alone to either vomit or receive an anti-emetic. Equivalently, a CR rate of 75% is anticipated with ondansetron alone.

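### Exploratory cross-over model in 15.4.2: the period-by-treatment interaction is read as constancy of the rolapitant effect, but it cannot be separated from carry-over or a sequence difference

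*Combined protocol and SAP*

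**What the plan says.** Section 15.4.2 makes the primary CR analysis a chi-square test between regimens over the first 2 weeks of treatment. It then adds an exploratory generalized linear model with a logit link, allowing for within-patient correlation, to be "used to assess the impact of period, treatment, and their interaction". The stated aim is: "The purpose of this latter analysis is to assess whether the incremental effect of combination treatment relative to ondansetron alone is the same" whether rolapitant falls in the first or the second 3-week period. The one caution attached is that "this test will have low power to detect a clinically meaningful interaction effect". Carry-over is not mentioned for CR.

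On the design, 9.6 says "A 1:1 allocation ratio will be used" for the two sequences, and 15.7.1 says "Sequence B involves a 3-week regimen of rolapitant (day 1 only) and daily ondansetron followed by a 3-week regimen of daily ondansetron". No washout between the periods is described. Section 9.7 justifies the single dose as giving "antiemetic coverage for 3 weeks of radiation (3-half-lives for rolapitant"). Section 7.2 gives a rolapitant half-life of 169 to 183 hours and describes an active metabolite: "the mean half-life of M19 was 158 hours".

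**The concern.** Two sequences and two periods yield four cell means. An intercept, a period effect, a treatment effect and their interaction use up all four. If residual rolapitant protects Sequence B patients in weeks 4 to 6, the second-period difference between regimens shrinks even when rolapitant works equally well in both periods. That shrinkage falls entirely into the interaction term, which 15.4.2 says it will read as a statement about whether the increment is constant.

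The caution about power does not cover this. Low power is cured by more patients, and this confounding is not. At stake is the interpretation of the exploratory model: a smaller period-2 difference could be reported as rolapitant helping less when given later, when it may reflect only what was left from day 1.

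**Working it through.** **1. The plan's own half-life count.** From the Sequence B dose (day 1) to the start of ondansetron alone (day 22) is 21 × 24 = 504 h. With the 170 h of 9.7, 504/170 = 2.96, which reproduces the stated 3 half-lives. Over 169 to 183 h the range is 2.98 down to 2.75.

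**2. Drug remaining at the switch.** Fraction left = 0.5^(504/half-life).
- Parent drug, 169 h: 0.5^(504/169) = 12.7%, or 22.8 mg of 180 mg.
- Parent drug, 183 h: 0.5^(504/183) = 14.8%, or 26.7 mg.
- M19, relative to its peak and assuming simple terminal decay from Tmax: 0.5^((504−120)/158) = 18.6% with the 120 h Tmax in 7.2, or 0.5^((504−168)/158) = 22.9% with the 168 h that 7.2 also gives for healthy subjects.

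These are values at the switch and they keep falling. By 35 days after the dose, parent drug is at 0.5^(840/169) = 3.2% to 0.5^(840/183) = 4.2%.

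**3. What the interaction estimates.** On the logit scale let μ be the baseline, π the period effect, τ the rolapitant effect, δ a true change in that effect in period 2, λ the carry-over into Sequence B period 2, and σ a difference between the sequence groups (B minus A).

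| Cell | Log-odds of CR |
|---|---|
| A, period 1 | μ |
| A, period 2 | μ + π + τ + δ |
| B, period 1 | μ + τ + σ |
| B, period 2 | μ + π + λ + σ |

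Interaction = (A2 − B2) − (B1 − A1) = (τ + δ − λ − σ) − (τ + σ) = δ − λ − 2σ.

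Only this combination is estimable. As a check, the four-cell design matrix for intercept, period, treatment and interaction has rank 4, and still has rank 4 after a carry-over column or a sequence column is added. The carry-over column equals period minus period × treatment in every row, so neither the decadron covariate nor a larger sample separates them.

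**4. Two explanations, the same data.** Take the plan's rates of 75% and 90%: logit(0.75) = 1.099, logit(0.90) = 2.197, so τ = 1.099 and the odds ratio is 3.00.
- Constant effect, no period effect, carry-over λ = 0.549 (half of τ): CR in A1, A2, B1, B2 is 75%, 90%, 90%, 83.9%.
- No carry-over, period effect +0.549, true interaction δ = −0.549: the same four rates.

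**5. How large the effect could look.** Constant true odds ratio 3.00, with carry-over assumed as a share of τ. Period-2 odds ratio = exp(τ − λ).

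| Assumed carry-over | CR in Sequence B, period 2 | Period-2 odds ratio | Ratio of odds ratios |
|---|---|---|---|
| 0% | 75.0% | 3.00 | 1.00 |
| 25% | 79.8% | 2.28 | 0.76 |
| 50% | 83.9% | 1.73 | 0.58 |
| 100% | 90.0% | 1.00 | 0.33 |

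**6. What a non-significant interaction would mean.** Large-sample Wald test, two-sided 0.05, 57 patients (28.5 per sequence). Variance = the sum over the two sequences of [v₁ + v₂ + 2ρ√(v₁v₂)]/28.5, with v = 1/[p(1−p)] in each cell and within-patient correlation ρ assumed between 0 and 0.5. For half carry-over the standard error is 1.107 (ρ = 0) to 1.347 (ρ = 0.5) against an effect of 0.549, giving power of 7% to 8%. For full carry-over, power is 12% to 16%.

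**The case against.** The best defence is that little depends on this model. It is labelled exploratory. The primary test compares the sequences in the first 2 weeks, before anyone crosses over. Sections 5.11 and 15.7.1 explain the cross-over as a way to let patients state a preference. All of that stands, and it limits the consequence. The plan is also aware of carry-over elsewhere: 15.5.2 makes the paired TSQM-9 comparison conditional on its absence, without naming a test, and 15.5.1 explores whether sequence influences preference. Neither supplies the missing statement for CR.

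Three stronger readings are tempting, and the documents do not support them.
- *A pooled cross-over odds ratio will be biased towards 1.* No such estimate is promised. The planned model includes the interaction. If period 1 is the reference level, its treatment coefficient is the period-1 effect, which carry-over does not touch.
- *The interval breaks the protocol's own clearance standard.* Exclusion 17 in 5.4 asks for no test drug "within 30 days or 5 half-lives of the biologic activity of the test drug, whichever is longer", but it concerns drugs from other studies. Exclusion 7 is specific to prior rolapitant and uses 21 days, the same as the day-1 to day-22 interval.
- *The pharmacokinetics prove a carry-over of antiemetic effect.* They show residual exposure. Section 7.2 says the link between receptor occupancy and clinical efficacy is not established and speaks of 5 days of protection from one dose. The dose evidence in 7.2.2 is mixed: 20 mg was active in the post-operative study, while CR at doses below 200 mg was not significant in the highly emetogenic chemotherapy study. Section 9.7 claims coverage up to the switch, not beyond it.

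It is also fair that randomization makes σ zero in expectation, so a sequence difference would arise only by chance. Carry-over is the systematic part.

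**Conclusion.** The stated purpose of the exploratory model cannot be met in this design. The interaction estimates δ − λ − 2σ, and no sample size or covariate isolates δ. This is algebra and needs no pharmacokinetic assumption.

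The documents' own figures make carry-over plausible: 12.7% to 14.8% of parent drug on day 22, plus active M19, and no washout. Its clinical size is unknown. The period-2 odds ratios of 2.28, 1.73 and 1.00 are therefore illustrations that rest on assumed carry-over shares, a constant true odds ratio of 3.00 and the logit scale. They are not forecasts.

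The correction is worth making because it changes what the analysis may claim. A reader should not infer that the primary result is compromised: the period-1 chi-square test is untouched.

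**What to change.** In 15.4.2, replace the sentence giving the purpose of the exploratory model with text to this effect:

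*With two sequences and two periods, the period-by-treatment interaction jointly reflects any change in the treatment effect between periods, any carry-over of rolapitant into the second period of Sequence B, and any difference between the sequence groups. It will not be interpreted as effect modification, and a non-significant result will not be interpreted as absence of carry-over. Conclusions about the treatment effect on CR will rest on the between-sequence comparison in period 1. The period-2 contrast will be described separately, as rolapitant on day 22 versus rolapitant three weeks earlier.*

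The existing caution about power can stay beside it. The cost is a wording change, and the exploratory analysis claims less. No new data and no change to the schedule, sample size or primary analysis are needed.
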